#### **2.4.2. Laboratory Evaluations**

Laboratory results for hematology, chemistry and urinalysis will be presented in data listings. Observed values and change from baseline values for hematology and chemistry parameters will also be summarized using descriptive statistics. Observed values for urinalysis will be summarized using frequency counts.

Values outside the normal range will be presented in a separate data listing.

#### **2.4.3. Vital Signs**

Blood pressure, heart rate, and respiration rate will be measured at each visit. Observed and change from baseline values will be summarized using descriptive statistics. All vital signs will be shown in data listings.

#### **2.4.4. Physical Exam and Nasal Inspection**

Physical examination and nasal inspection data will be presented in data listings.

#### **2.4.5. 12-Lead Electrocardiogram**

ECG Diagnosis, ventricular rate, RR interval, PR interval, QRS interval, QT Interval and QTcF Interval will be collected each time the ECG is performed. Observed and change from baseline values will be summarized using descriptive statistics. All electrocardiogram results will be shown in data listings.

#### **2.4.6. Ambulatory Blood Pressure Monitoring (ABPM)**

The average 24-hour, daytime (8AM to 4PM), waking hours (6AM to 10PM) and nighttime (10PM to 6AM) systolic and diastolic measurements will be listed and summarized. Observed and change from baseline values will be summarized using descriptive statistics. All ABPM parameters will be shown in data listings.

### **2.5. Efficacy**

The collected data will be summarized using descriptive statistics (sample size, mean, standard deviation, median, minimum and maximum) or frequency counts, where appropriate, by treatment group and overall.

Area under the Curve (AUC) values will be derived using the trapezoidal rule with each observed value being an endpoint for the trapezoids. Thus (assuming that an

individual has all of the expected measurements), the AUC for 0 to 120 minutes Post NAC (as an example) would be derived by adding the areas of the following trapezoids: 0 to 15 minutes, 15 to 30 minutes, 30 to 45 minutes, 45 to 60 minutes, 60 to 90 minutes and 90 to 120 minutes.

### **2.5.1. Total Nasal Symptom Score (TNSS) During NAC**

The total nasal symptom score during NAC is collected for part 2 only.

The total nasal symptom score will be summarized by each individual score (nasal congestion, sneezing, nasal itching and rhinorrhea) and total nasal symptom score for each time point by each treatment group individually and both active groups combined.

The individual items will be summarized using frequency counts for each time point. Observed values and change from baseline will be summarized. A Cochran-Mantel-Haenszel test will be conducted at each time point to test for treatment effect.

Pre-NAC adjusted value is defined as the observed value minus the 0 minutes prior NAC value.

The total nasal symptom score will be summarized using summary statistics for:

- The observed Total Nasal Symptom Score at each time point,
- The Pre-NAC adjusted Total Nasal Symptom Score at each time point,
- The observed individual symptom scores (nasal congestion, sneezing, nasal itching and rhinorrhea) at each time point,
- The Pre-NAC adjusted individual symptom scores (nasal congestion, sneezing, nasal itching and rhinorrhea) at each time point
- The Observed Area Under the Curve in Total Nasal Symptom Score from 0 to 120 minutes Post NAC, and
- The Pre-NAC adjusted Area Under the Curve in Total Nasal Symptom Score from 0 to 120 minutes Post NAC.
- The Observed Area Under the Curve for each individual symptom score (nasal congestion, sneezing, nasal itching and rhinorrhea) from 0 to 120 minutes Post NAC, and
- The Pre-NAC adjusted Area Under the Curve for each individual symptom score (nasal congestion, sneezing, nasal itching and rhinorrhea) from 0 to 120 minutes Post NAC.
- Nasal symptom-free response rate (defined as a value of 0) for each individual symptom score and the Total Nasal Symptom Score at Visit 4.

For Part 2, observed values and change between Visits 3 and 4 will be summarized for the indicated items.

In addition to the items indicated above, the following items will also be analyzed:

- Percent of subjects with 25% reduction in Total Nasal Symptom Score between Visits 3 and 4.

- Percent of subjects with 50% reduction in Total Nasal Symptom Score between Visits 3 and 4.

For Total Nasal Symptom Score and Area Under the Curve analyses, an Analysis of Covariance with treatment as the factor and Visit 3 value as a covariate will be used to test for treatment effect at Visit 4.

For response rates, individual item scores and percent reduction, a Cochran-Mantel-Haenszel test will be conducted to test for treatment effect.

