- Subjects will be asked to report for a screening visit (Visit 1) and if all inclusion/exclusion criteria are met, subjects will be asked to report for a NAC titration (ragweed pollen nasal allergen titration) visit to administer a single provocative challenge dose for each subject (Visit 2). Subjects will then return 14 days after the washout period for basic health checks and baseline assessments (intranasal fluid, TNSS, PNIF, intranasal nitric oxide, and have a nasal inflammation score) followed by confirmatory NAC (NAC#1) (Visit 3). During this time subjects will use a study diary to complete TNSS at -30 (30 minutes prior to NAC), 0 (baseline prior to NAC), 15, 30, 45, 60, 90, and 120 minutes. PNIF at -30, 0, 15, 30, 60, and 120 minutes will also be obtained. TNSS is the sum of four individual symptom scores (running nose, congestion, itchy nose, and sneezing) rated on a four point scale (0-3). Subjects are required to meet the minimum qualifying TNSS score of a change of 6/12 from their baseline score, on at least 2 diary cards. Subjects will also provide samples for intranasal fluid at 0, 20, and 60 minutes, measure intranasal nitric oxide (nNO) and have a nasal inflammation score assessed by the investigator using a nasal otoscope at 0 and 120 minutes, in addition to blood collection at 120 min for biomarkers. Subjects meeting the requirement will be randomized to one of the three treatment arms. Randomization will be 1:1:1 so that equal number of subjects will be treated in each arm of the study. Subjects will then be trained on the use of the nasal spray, and have their first dose of treatment on site (self-dosing). Subjects will remain onsite for observation for 1 hour post dosing. Subjects will then be dispensed study medication for 14 days of at home dosing. While at home, subjects will dose twice daily (am and pm), and record their dosing, and any occurrence of an AE and TNSS using a study diary.

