### **1.3. Trial Objectives and Purpose**

The primary objective of the study is to assess the safety and tolerability of B244 relative to vehicle in healthy volunteers during 14 days of treatment and up to 28 days of follow-up.

The secondary objectives of the study are:

- To evaluate the efficacy of B244 relative to vehicle in treating Total Nasal Symptom Score (TNSS) in subjects with seasonal allergic rhinitis evaluated in a nasal allergen challenge model as a prophylaxis therapy after 14 days of treatment.
- To evaluate the safety and tolerability of B244 relative to vehicle in subjects with allergic rhinitis after 14 days of treatment.
- To evaluate the efficacy of B244 relative to vehicle in treating individual nasal symptom scores in subjects with allergic rhinitis evaluated in a nasal allergen challenge model as a prophylaxis therapy after 14 days of treatment.

The exploratory objective is to test the hypothesis that B244 inhibits airway inflammation driven by nasal allergen challenge.

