## **2. Detailed Statistical Methods**

### **2.1. General Statistical Methods**

This is a two-part study. Each of the two parts have 2 levels of active therapy ( $1 \times 10^9$  cells/ml and  $4 \times 10^9$  cells/ml) versus vehicle. The listings and tables will be presented separately for each of the two parts.

The collected data will be summarized using descriptive statistics (sample size, mean, standard deviation, median, minimum and maximum) or frequency counts, where appropriate, by treatment and overall.

For continuous variables, an Analysis of Covariance (ANCOVA) may be performed to test for significant differences between treatment groups. For discrete variables, the Cochran-Mantel-Haenszel Row Mean Score test will be used to test for significant differences between treatment groups.

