#### **2.7. Sample Size and Power Considerations**

Part 1 (safety and tolerability evaluation in healthy volunteers) will enroll 24 subjects. Up to 12 subjects per dose cohort (n=8 active, n=4 vehicle) will be enrolled, with a target of 20 subjects completed (10 subjects per dose cohort; n=7 active, n=3 vehicle) assuming a 16.7% drop out rate. The two dose cohorts are  $1 \times 10^9$  cells/ml and  $4 \times 10^9$  cells/ml.

Part 2 (preliminary efficacy evaluation in subjects with a history of SAR to ragweed pollen) will enroll 42 subjects. Up to 14 subjects per arm ( $1 \times 10^9$  cells/ml;  $4 \times 10^9$  cells/ml or vehicle) will be enrolled, with a target of 12 subjects per arm for a total of 36 subjects completed, assuming a 10-15% drop-out rate.

The sample size for this study is not based on statistical considerations.

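### The SAP's efficacy tests are most naturally read as global three-arm tests; no B244-versus-vehicle contrast, adjusted difference or confidence interval is specified, although the objective is B244 relative to vehicle

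*SAP*

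**What the plan says.** The SAP's first secondary objective (1.3) is "To evaluate the efficacy of B244 relative to vehicle in treating Total Nasal Symptom Score (TNSS"), and protocol 3.2 says the same. On the number of groups, SAP 2.1 says "Each of the two parts have 2 levels of active therapy", set against vehicle. Part 2 therefore compares three arms.

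The stated tests are these:

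- **Symptom score and AUC (SAP 2.5.1):** "an Analysis of Covariance with treatment as the factor and Visit 3 value as a covariate will be used to test for treatment effect". The outcome tested is the Visit 4 value.
- **PNIF and intranasal nitric oxide (SAP 2.5.2 and 2.5.4):** an ANCOVA of the same form.
- **Item scores, response rates and percent-reduction endpoints (SAP 2.5.1):** a Cochran-Mantel-Haenszel test for treatment effect. SAP 2.1 describes the general rule for discrete variables: "the Cochran-Mantel-Haenszel Row Mean Score test will be used to test for significant differences between treatment groups".

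SAP 2.5.1 also summarises the challenge symptom scores "by each treatment group individually and both active groups combined", but attaches no test to the combined group. SAP 2.11 leaves the form of the algorithms to SAS defaults.

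Protocol section 13 plans something different: a one-sided two-sample z-test for continuous endpoints and Fisher's exact test for frequencies. It does not say which pairs of arms are compared. The SAP does not explain the change.

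**The concern.** A three-level treatment factor, tested by default, asks whether any arm differs from any other. The row mean score test across three arms asks the same kind of question. Neither asks whether B244 differs from vehicle. A significant result would have no direction and no size, and a contribution from dose against dose cannot be separated from a contribution from B244 against vehicle.

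SAP 2.7 says "The sample size for this study is not based on statistical considerations". The most useful product of Part 2 is therefore an estimated difference from vehicle with its precision, and the SAP does not ask for one. Because no contrast is named, the choice among low dose, high dose and pooled B244 stays open until after unblinding.

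**Working it through.** **Inputs from the documents.** SAP 2.7 plans Part 2 "with a target of 12 subjects per arm for a total of 36 subjects completed, assuming a 10-15% drop-out rate". Protocol section 5 gives the allocation: "Randomization will be 1:1:1 so that equal number of subjects will be treated in each arm of the study". That is n = 12 in each of three arms. With three arm means and one covariate slope, the residual df are 36 − 3 − 1 = 32.

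**Assumptions.** Neither document gives an alpha, SD, effect size or target power, so there is no power figure to reproduce. I assume two-sided 0.05 and express effects in residual SD units. Covariate imbalance between arms is ignored.

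**Step 1: precision of the missing estimates.** The critical value is t(0.975, 32) = 2.037.

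- One dose minus vehicle: SE = √(1/12 + 1/12) = 0.408; half-width 2.037 × 0.408 = 0.83 SD.
- Pooled B244 minus vehicle: SE = √(1/12 + 1/24) = 0.354; half-width 2.037 × 0.354 = 0.72 SD.

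**Step 2: what a significant global test can mean.** The noncentrality is λ = 12 × Σ(arm mean − grand mean)². Suppose one dose lies e above vehicle and the other e below, so the average B244 effect is zero. Then λ = 24e².

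| e (SD) | λ | Global test significant |
|---|---|---|
| 0.3 | 2.16 | 22% |
| 0.5 | 6.00 | 54% |
| 0.6 | 8.64 | 71% |

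This is a constructed illustration of what the test responds to. Nothing in the documents suggests opposite effects.

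**Step 3: power, as a conditional example only.** The global test uses noncentral F(2, 32). A single contrast uses noncentral F(1, 32) with λ = (contrast)²/SE², where SE² is 0.125 for pooled and 0.1667 for one dose. Let d be the larger dose effect.

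- *Equal effects:* λ = 8d² for both the global and the pooled test.
- *Low dose has half the effect:* global λ = 6d²; pooled λ = (0.75d)²/0.125 = 4.5d².
- *Only one dose works:* global λ = 8d²; pooled λ = (0.5d)²/0.125 = 2d².
- *A single dose with effect d against vehicle:* λ = d²/0.1667 = 6d².

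| Shape | d (SD) | Global | Pooled | Difference (points) |
|---|---|---|---|---|
| Equal | 0.3 | 10.3% | 13.1% | +2.8 |
| Equal | 0.5 | 20.9% | 27.9% | +7.0 |
| Equal | 0.8 | 47.5% | 59.3% | +11.8 |
| Equal | 1.0 | 67.4% | 78.3% | +11.0 |
| Equal | 1.5 | 96.0% | 98.4% | +2.4 |
| Half effect, low dose | 0.8 | 36.9% | 37.7% | +0.8 |
| Half effect, low dose | 1.0 | 54.2% | 53.9% | −0.3 |
| One dose only | 0.8 | 47.5% | 19.5% | −27.9 |
| One dose only | 1.0 | 67.4% | 27.9% | −39.5 |

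(Differences are taken before rounding.) With equal effects the gain peaks at 11.9 points, at 0.85 SD. If only one dose works, that dose against vehicle, unadjusted, has 47.6% at 0.8 SD and 66.1% at 1.0 SD, about equal to the global test. With a Bonferroni correction for two doses these fall to 36.0% and 54.4%.

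**The case against.** The strongest reply has three parts.

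First, the SAP never says that only a global test will be run. Treatment as a factor neither specifies nor excludes contrasts. This stands as a matter of wording: the 2-df test is the natural reading under SAS defaults, not an explicit statement.

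Second, efficacy here is secondary and preliminary. The planned tables give n, mean and SD by arm, including the change between Visits 3 and 4, and for challenge symptom scores also for the combined actives. A reader could see the direction and calculate crude differences and intervals. This also stands, and it limits the consequence. It does not supply the covariate-adjusted difference, which is what the ANCOVA can provide.

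Third, a reader might infer that the global test simply wastes about 11 points of power and that a pooled contrast should replace it as the main test. The documents do not support that. They give no alpha, SD or effect size, and the figure needs equal dose effects of roughly 0.7 to 1.0 SD. The concentrations differ fourfold, so unequal effects are plausible, and then the pooled gain disappears or becomes a large loss. Making the pooled contrast lead is a trade-off for the sponsor to decide in advance, not a correction.

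**Conclusion.** The point holds as an omission. On the natural reading, SAP 2.5.1, 2.5.2 and 2.5.4 test a global difference among three arms and specify no contrast with vehicle, adjusted difference or interval. Followed as written, they do not answer the stated objective, and they drop the two-sample form of protocol section 13 without a reason.

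The unreported precision is about ±0.83 residual SD per dose and ±0.72 pooled, given 12 completers per arm and a 95% interval. These intervals are wide, which is itself information that the next trial needs.

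No general power loss can be claimed. Under the assumptions above, the pooled contrast gains about 2 to 12 points with equal effects of 0.3 to 1.5 SD. It gains essentially nothing at 0.8 to 1.0 SD if the low dose has half the effect, and loses about 28 to 40 points over the same range if only one dose works. The recommendation rests on interpretability and estimation. It should be made, but it does not threaten the primary objective, which is safety in Part 1.

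**What to change.** In SAP 2.5.1, 2.5.2 and 2.5.4, keep the ANCOVA with the Visit 3 covariate and add:

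1. Each B244 dose minus vehicle, and pooled B244 minus vehicle, as LS mean differences with 95% CIs.
2. For the CMH endpoints, matching per-dose and pooled comparisons with vehicle.
3. A statement that the efficacy conclusion rests on these comparisons and not on the global p-value.
4. Before unblinding, which contrast leads, whether it is one- or two-sided, and how multiplicity is handled, with a sentence explaining the departure from protocol section 13.

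The cost is SAP text and contrast statements in models already planned, with no new data, visits or subjects. The downside is a few more reported comparisons, which should be labelled exploratory or adjusted for multiplicity.

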### **1.3.2. Secondary Endpoints**

The secondary endpoints are:

- Change in TNSS from baseline to 14 days of prophylaxis treatment.
- Change in subjective nasal symptom scores of nasal congestion, rhinorrhea, nasal itching and sneezing from baseline to 14 days of prophylaxis treatment.
- Nasal symptom-free response rate within each individual symptom score and TNSS after 14 days of prophylaxis treatment.
- Safety and tolerability will be assessed in subjects with allergic rhinitis by reporting of AEs, physical examination and vital signs (blood pressure, heart rate, respiratory rate) during 14 days of treatment (Part 2).

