### **2.5.3. Nasal Inflammation Score**

The nasal inflammation score is collected in both Part 1 and Part 2, but the timing of the collection is different between the parts. For Part 1, the data is collected for observation only. For Part 2, the data is collected as an exploratory efficacy endpoint.

Pre-NAC adjusted value is defined as the observed value minus 0 minutes prior NAC value.

The nasal inflammation score will be summarized using summary statistics for:

- The observed value at Pre-NAC and 120 minutes Post-NAC, and
- The Pre-NAC adjusted value at 120 minutes Post-NAC,

For Part 2, observed values and change between Visits 3 and 4 will be summarized for the indicated items.

The collected data will be summarized using frequency counts at each time point in which the assessment was collected. Observed values will be summarized. A Cochran-Mantel-Haenszel test will be conducted at each post-baseline visit to test for treatment effect.

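### Time-point tests of the individual symptom scores, and the test of the nasal inflammation score, omit the Visit 3 value that the SAP uses for the other challenge outcomes, at some cost in precision

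*SAP*

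**What the plan says.** SAP 1.3.2 lists as a secondary endpoint "Change in subjective nasal symptom scores of nasal congestion, rhinorrhea, nasal itching and sneezing from baseline to 14 days" of treatment. SAP 2.5.1 first says of these items: "The individual items will be summarized using frequency counts for each time point. Observed values and change from baseline will be summarized". It continues: "A Cochran-Mantel-Haenszel test will be conducted at each time point to test for treatment effect". It closes the section with: "For response rates, individual item scores and percent reduction, a Cochran-Mantel-Haenszel test will be conducted to test for treatment effect". Neither sentence names a covariate, a stratum or the response variable. SAP 2.1 identifies the statistic, for discrete variables in general, as the row mean score version.

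The total score is handled differently. "For Total Nasal Symptom Score and Area Under the Curve analyses", the SAP says, "an Analysis of Covariance with treatment as the factor and Visit 3 value as a covariate will be used". The list of outcomes above that sentence includes "The Observed Area Under the Curve for each individual symptom score", and the pre-challenge adjusted version of it, so the individual-symptom AUCs come under the adjusted analysis. PNIF (2.5.2) and nitric oxide (2.5.4) also take the Visit 3 value as covariate.

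For the nasal inflammation score, an exploratory endpoint in Part 2, SAP 2.5.3 says: "A Cochran-Mantel-Haenszel test will be conducted at each post-baseline visit to test for treatment effect". The paragraph holding that test mentions only observed values. Changes between Visits 3 and 4 are summarized for the items and for inflammation, but no test is attached to them.

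**The concern.** Each symptom is scored at the same minutes after the challenge at Visit 3 and at Visit 4 (protocol section 5), and inflammation is graded at 0 and 120 minutes at both visits. A matching pre-treatment score is therefore available for every Visit 4 score. Leaving it out puts stable differences between subjects into the error term. With about 12 completers per arm, it also lets chance imbalance at Visit 3 pass into the treatment comparison.

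The result is an uneven plan. Congestion is adjusted for Visit 3 as an AUC and as part of TNSS, but not at any single time point. Total and item results at the same minute could then differ partly because they were analysed differently. Inflammation has no AUC, so it has no adjusted test at all.

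**Working it through.** **Inputs from the documents.** Part 2 has three arms allocated 1:1:1, with a target of 12 completers per arm (SAP 2.7; protocol section 5). Items and inflammation are scored 0-3 (protocol 11.15, 11.16). The only planning figure is enrolment, and it reproduces: 36/(1 - 0.10) = 40 and 36/(1 - 0.15) = 42.4, rounded up to 43, against 42 planned; the implied dropout is 1 - 36/42 = 14.3%. No effect size, SD or power is stated, and SAP 2.7 says that the size was not set on statistical grounds.

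**Assumptions.** Two-sided 0.05 (the SAP states no level; protocol section 13 has a one-sided z-test for continuous endpoints), the effect sizes, the category cut-points, and a range for the Visit 3 to Visit 4 correlation ρ.

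**Step 1: formula.** Relative to no adjustment, ANCOVA leaves residual variance 1 - ρ², and a change score has variance 2(1 - ρ). The change score is therefore worse than no adjustment whenever 2(1 - ρ) > 1, that is, ρ < 0.5. The unadjusted number per arm that matches 12 adjusted is 12/(1 - ρ²). For a 1-SD difference between two arms, power = Φ(√(12/2)/k - 1.96), where k² is the variance factor. Unadjusted: Φ(2.449 - 1.96) = 0.69. At ρ = 0.5: Φ(2.449/0.866 - 1.96) = 0.81.

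| ρ | Variance, ANCOVA | Unadjusted n per arm matching 12 | Power, ANCOVA | Power, change |
|---|---|---|---|---|
| 0.2 | 0.96 | 12.5 | 0.71 | 0.49 |
| 0.4 | 0.84 | 14.3 | 0.76 | 0.61 |
| 0.5 | 0.75 | 16.0 | 0.81 | 0.69 |
| 0.6 | 0.64 | 18.8 | 0.87 | 0.78 |
| 0.8 | 0.36 | 33.3 | 0.98 | 0.97 |

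**Step 2: simulation on the 0-3 scale.** 20,000 trials per setting, 12 per arm. A correlated normal pair is cut at its 10th, 35th and 70th percentiles to give scores of 0-3. At Visit 4 the latent shifts are 0 (vehicle), -0.6 and -1.0. The row mean score statistic is (N - 1) × between-arm SS / total SS, referred to chi-square on 2 df. ANCOVA is an F test on 2 and 36 - 3 - 1 = 32 df.

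| Observed-score correlation | CMH, Visit 4 score | ANCOVA with Visit 3 | CMH on change |
|---|---|---|---|
| 0.00 | 48.5% | 49.0% | 25.8% |
| 0.17 | 48.3% | 50.1% | 30.2% |
| 0.35 | 48.5% | 54.0% | 37.5% |
| 0.53 | 48.6% | 63.0% | 50.8% |
| 0.72 | 48.3% | 79.1% | 71.7% |

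With no treatment effect, all three tests reject in 4.2% to 5.1% of trials.

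**Step 3: rank ANCOVA.** A separate simulation (3,000 trials per setting, both doses shifted by 0.7 points) gave, at correlations of 0.21, 0.47 and 0.66, power of 48%, 42% and 33% for unadjusted CMH, 48%, 48% and 53% for rank ANCOVA, and 50%, 52% and 56% for ANCOVA. The fall in the unadjusted figures suggests that the spread of scores grew with the correlation, so the methods should be compared only within one correlation.

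**Step 4: selection.** Protocol 6.3 requires a 6-point rise in TNSS after NAC #1 on at least two diary cards. A simplified version (Visit 3 sum of at least 6 at one time, assumed variances, 0.7-point shift) lowered the item correlation from 0.44 to 0.33 and the gain from about 8 to about 4.5 points. In a higher-correlation case it lowered the correlation from 0.62 to 0.51 and the gain from about 14 to about 11 points.

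**The case against.** The best defence is that the SAP applies its own rule. Section 2.1 assigns CMH row mean score tests to discrete variables, and a 0-3 score is discrete. That stands: the choice has a recognised reason. It does not prevent adjustment, because rank ANCOVA applies the same statistic to residual ranks.

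A reader might infer more than the documents support:

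- *That the individual symptoms are never adjusted for Visit 3.* They are, through their AUCs under 2.5.1. Only the time-point tests are affected.
- *That inflammation is a component analysed differently from its total.* It is graded by a clinician and is not part of TNSS. It is also exploratory.
- *That the change endpoint goes untested.* The SAP does not say whether the item test uses the observed score or the change, and its reference to change from baseline there does not name the baseline. Under randomization, comparing Visit 4 means and comparing mean changes from Visit 3 also target the same treatment difference. For the items, this part of the point is under-specification.
- *That the test is biased.* Its null rejection rate in Step 2 is 4.5% to 4.7%.

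It is also fair to say that the correlation is unknown, that selection on Visit 3 response probably lowers it, and that these are secondary and exploratory endpoints in a study that makes no power claim. All of that limits the size of the point.

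**Conclusion.** The point holds as one of precision and specification. The time-point item tests (secondary) and the inflammation test (exploratory) name no Visit 3 term, although the score is collected and the SAP uses it for the related outcomes. Under the Step 2 assumptions, adjustment gains about 2 points of power at an observed correlation of 0.17 (50.1 - 48.3), 5.5 at 0.35 (54.0 - 48.5), 14 at 0.53 (63.0 - 48.6) and 31 at 0.72 (79.1 - 48.3), before any reduction from selection. At low correlation it costs essentially nothing.

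If the item test was meant for the change, that reading also needs amending: below a correlation of about 0.5 it has less power than no adjustment. The figures illustrate the direction and rough scale. They do not estimate this trial's power, because the correlation, effects and score distribution are all assumed.

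**What to change.** Amend SAP 2.5.1 and 2.5.3 before the Part 2 database lock, since SAP 2.6 places unblinding and analysis straight after it and a later choice could be driven by the data:

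1. Name the observed Visit 4 score as the response for the item tests and the 120-minute score for inflammation.
2. Add the same-time Visit 3 score as covariate, either by rank ANCOVA (row mean score test on residual ranks, which keeps the CMH framework) or by the ANCOVA already specified for TNSS. Choose one in advance.
3. Report the adjusted difference of each dose from vehicle with a 95% CI from the ANCOVA.
4. Keep the unadjusted CMH on the observed Visit 4 score as a sensitivity analysis.

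Do not adjust by stratifying CMH on the Visit 3 score. Four levels among 36 subjects average 36/4 = 9 per stratum, or 3 per arm, and some would be emptier.

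The cost is a change of SAP wording and a little programming. No new data are needed.
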